**Table 11: Overview of IPE Activities and Objectives**

Activity	Objective
Interviews with staff (LAs/nurses)	
Intervention:
 
 
1. To assess i] acceptability and ii] fidelity of the intervention.
 
2. To identify any evidence of mechanisms of change as outlined in developed programme theory.
 
3. To explore barriers and facilitators of service delivery (including contextual factors).
 
 
Trial methods:
 
 
1. To assess acceptability of randomisation.
 
2. To assess i] feasibility of data collection methods and ii] refinement needed.
 
3. To assess potential ethical/practical/statutory/legal barriers that impact recruitment and randomisation.
 
 
Indicative outcomes:
 
 
1. To assess perceived outcomes on service users receiving the intervention.
 
2. To examine any housing and health needs unmet by the intervention.
 

Interviews with service users	
Intervention:
 
 
1. To assess acceptability of the intervention.
 
2. What evidence is there for the mechanisms of change as identified in the programme theory?
 
3. To understand service user experiences of receiving the intervention.
 
 
Indicative outcomes:
 
 
1. To assess perceived outcomes for service users receiving the intervention.
 
2. To examine any housing and health needs unmet by the intervention.
 

Observation on intervention delivery	
Intervention:
 
 
1. To assess fidelity of the intervention delivery.
 
 
Trial methods:
 
 
1. To assess i] feasibility of data collection methods and ii] refinement needed.
 

Time and resource logbooks	
Intervention:
 
 
1. To assess fidelity of the intervention delivery.
 

Routinely collected contextual data (interim contact data including level of contact per service user, treatment, care or advice given)	
Indicative outcomes:
 
 
To assess perceived outcomes on service users receiving the intervention.
 
 
Intervention:
 
 
To assess acceptability of the intervention
 
To assess fidelity of the intervention delivery
 

Interviews with staff in LAs that opt to withdraw	
Trial methods
 
 
To assess any potential ethical, practical, statutory, or other legal barriers that impact retention of LAs.
 

### 11.2.2. Population

The population will be CGL/LA staff (outreach workers and nurses) and service users in four intervention and two control sites, and LA representatives from any site that opts to withdraw from the cRCT.

**Table 12: IPE Interview Inclusion and Exclusion Criteria**

Individual	Inclusion criteria	Exclusion criteria
Service Users	
 
People living on the streets (defined as seen sleeping on the streets on at least 6 separate occasions over a period of up to 6-months).
 
Sufficient level of conversational English.
 
	
 
People rough sleeping, not eligible to be included in routine data capture for the cRCT.
 
Incapable of giving informed consent.
 

Intervention Staff	
 
Outreach team workers and nurse practitioners delivering the outreach with a health specialism service in selected LAs.
 
Lead nurse supervising nurse practitioners.
 
Outreach team workers supporting nurses to complete outreach shifts.
 
	
 
Intervention staff that have not received the Test and Learn with health specialism bespoke training package (e.g. agency cover).
 

Usual Practice Staff	
 
Outreach team workers delivering usual practice in selected LAs.
 
	
 
Agency cover staff.
 

LA Representative	
 
LA site withdrawal confirmed in writing/notified via CHI.
 
	
 
LA staff/representative with no understanding or
 

	
 
LA site project lead or nominated staff representative involved in homelessness provision.
 
	sufficient knowledge of reasons for withdrawal.
--	--	---

### 11.2.3. Sampling strategy

A purposive sampling strategy will be used to identify a range of sites to ensure they are representative of a broad range of geographical areas (e.g. urban and rural) and population sizes and size of homeless population.

Service users accessing support from the local outreach service will be informed of the opportunity to take part in interviews and asked for expressions of interest. We will aim to interview a diverse range of service users by gender, age, and ethnicity across the whole sample of seven areas.

Sampling levels are guided by information power (Malterud et al., 2015) whereby a relatively small number of participants is justified by the specialist knowledge and information power that they hold, which would not be improved upon by continued recruitment.

All intervention sites will be asked to complete the time and resource logbooks.

**Table 13: IPE Sampling Size**

Activity	Sampling size n=
Observations	2 on-street shifts per site (5 intervention and 2 control sites) (N=14)
Intervention and control site interviews	2 staff per site (N=14) 3 service users per site (N=21)
Time and resource logbooks	8 intervention sites
Interviews with LAs that opt to withdraw	Up to a maximum of 8 interviews

### 11.2.4. Recruitment

- Service user interviews:

Individual interview participants will be recruited as follows in both intervention and control sites:

Wider Local Authority staff will be key gatekeepers. Staff will be briefed early in the study on the intention to interview service users and asked for their advice on approaching people. Staff will then be asked to gain informal expressions of interest from people they are supporting, which will then be followed up where possible during site visits by the research staff.

Outreach staff will introduce the researcher to interested participants who meet the inclusion criteria and are available at the time of on-site visit by the research staff member. The researcher will explain the purpose of the study and provide an information sheet, which can be read by the service user or read out by the researcher if preferred. The service user will be invited to ask any questions and, once these are addressed, the researcher will gain written consent for interview participation. This will then be confirmed verbally at the start of interview recording. Interviews will be conducted in a quiet space where possible in the context of on-street delivery, but in sight of LA staff at all times.

- Staff Interviews:

The evaluation team, CHI Project Manager, and LA Project Lead will identify and contact potential participants and distribute details of the research. Site staff will be approached by the evaluation team and asked if they are interested in taking part in an interview. Should any site withdrawals be received, LA Project Lead staff will be invited to take part in an interview or nominate a site representative with sufficient knowledge of reasons for withdrawal.

The evaluation team will provide potential participants with an information sheet and consent form to decide if they would like to take part in an interview. The evaluation team will follow-up to establish interest and arrange an online/telephone interview.

#### 11.2.5. Data collection

Routine data will be collected as per Section 8 of this protocol.

Semi-structured interview guides will be developed for staff and service user interviews. Different staff interview guides will be developed for intervention and control site staff. Topics will include:

**Intervention:**

- Descriptions of routine/intervention service delivery (including any associated costs to deliver these, e.g. material costs)
- Barriers and facilitators to delivery as intended
- Perceptions of mechanisms of change relating to the intervention
- Attitudes to service content and views on any additional service needs not being addressed

**Trial methods:**

- Attitudes towards randomisation methods
- Barriers and facilitators to randomisation and data collection methods
- Refinements to amended routine data collection tools
- Factors influencing withdrawal (where relevant)

**Indicative outcomes:**

- Perceptions of impacts of the intervention

For service users, interviews will include:

- Experience of receiving support, including barriers and facilitators to accessing services
- Perceptions of service content and any unmet needs
- Perceived mechanisms and impacts of the intervention

Observation data collection will be conducted in the format of field notes during site visits to capture any relevant contextual information as well as through a structured observation checklist based on developed programme theory of the intervention. Checklists will include reflections on numbers and types of interactions with service users, factors within the geographical and local context that impact on intervention delivery, fidelity of delivery based on the types of support offered to service users, quality and consistency of the intervention delivered by staff.

Intervention staff will be asked to complete a time and resource logbook proforma which will outline resource spent on various intervention components.

### **11.3. Data Analysis**

Routine contextual data will be thematically coded to understand nurse and service user interactions, e.g. treatment, care, and advice given and service user responses, as well as perceived acceptability of the intervention and fidelity of delivery.

Interview data will be transcribed verbatim and field notes will be transferred electronically and expanded where relevant. Qualitative data will be analysed using deductive and inductive coding. Initial coding will be aligned with the research questions as a means of organising the data for subsequent interpretation. Using a mixed methods approach we will undertake a thematic content analysis, in which themes will be identified and organised into an analytical framework.

Observational checklist and resource logbook data will be analysed using content analysis and will feed into the overall analytical framework. We expect this to include themes from the optimisation (Phase 1), which may be further developed and refined, and additional 'new' themes that arise from Phase 2 of the trial. NVivo 12 software will be used to process this data. Each portion of analysis will be reviewed by a second researcher and discussed within the team to ensure rigour.

## 12. ECONOMIC EVALUATION

### 12.1. Aim, Objectives and Research Questions

**Aim:** The economic evaluation seeks to understand the extent to which the economic and societal benefits of the intervention offset the associated costs of undertaking it.

**Objective:** The overall objective is to better understand to what extent the outreach with a health specialism service achieved good value for money.

**Research Question:** To what extent did the benefits of the outreach with a health specialism service exceed its costs?

### 12.2. Research Design and Methods

#### 12.2.1. Overall approach

The economic evaluation will utilise a cost-benefit analysis (CBA) to understand whether the outreach programme offered value for money – that is whether the monetised benefits of the programme exceeded the associated costs. The CBA framework set out below aligns with the principles set out in the HM Treasury Green Book (The Green Book, 2022).

To undertake a CBA, both the benefits and costs must be expressed in monetary terms. Sections 12.2.4 and 12.2.5 set out the expected costs and the benefits, and critically, the means of monetising the benefits.

We note that for this CBA to be of maximum relevance for MHCLG, we will strive to align its parameters and assumptions as much as possible with existing cost-benefit analyses conducted by MHCLG. Information on these assumptions is not available at the time of writing, so this protocol outlines the evaluation team’s current assessment. However, if more appropriate assumptions on consensus-based values are identified by MHCLG, these will be utilised for the evaluation. These could be described in a future protocol amendment. We also acknowledge that one wider goal of the pilot is to help bring more consensus to accepted parameters and definitions of such avoided costs/benefits in the homelessness sphere.

#### 12.2.2. Relevant alternatives/counterfactuals

There are alternative methods of undertaking value-for-money assessments:

- Cost effectiveness analysis – This is used when the benefits of a programme can be aggregated into common units, but the benefits cannot be monetised. Many health programmes utilise a CEA analysis where the intervention can be aggregated to a single non-monetisable outcome, e.g. cost per avoided cardiac event.

- Cost consequence analysis – This is used when the benefits of a programme cannot be aggregated into common units and instead are presented separately alongside their associated costs to provide a comprehensive summary of costs and effects.
- Cost benefit analysis – This is used when the benefits of a programme can be monetised and presented alongside their associated costs. This allows researchers to provide an assessment of costs and benefits summarised in monetary terms. Note, however, that some benefits or costs might not be monetisable and will be described as such.

Following guidance in the HM Treasury Green Book, we will attempt to conduct a social cost-benefit analysis as the recommended approach to undertake value-for-money assessments.

A *counterfactual* identifies what would have happened in the absence of the programme. Anything observed over and above the counterfactual we consider ‘additional’. It is these additional benefits which represent economic and societal gains and are what we seek to understand the monetary value of. In the context of this trial, we consider the control arm to provide the counterfactual. The random assignment of areas to each arm somewhat improves the credibility that observed differences in outcomes (i.e. housing stability and security as well as health benefits) can be attributed to the outreach with health specialism programme. Furthermore, the inclusion of other characteristics and controlling for baseline differences in outcomes will help to further strengthen the robustness of the counterfactual. Therefore, the economic evaluation will use parameters that account for baseline imbalances in line with the analytical approach described in Section 10.4.

### 12.2.3. Time horizons

The HM Treasury Green Book stipulates that the costs and benefits should be calculated over the lifetime over which the benefits are expected to last.

In the case of the outreach programme, the timings are as follows: the service runs for a period of 17 months from January 2025 to May 2026, baseline data collection takes place between January 2025 and October 2025 (ten months), with outcome data collection phased over most of the period of service delivery, ending in April 2026. For each individual, in treatment or control, there is baseline data collection followed by a data collection three months later (mid-period) and then a final six-month data collection. From a CBA perspective this means that the live period in question is only six months since first contact, reducing issues of discounting and net present value.

There is limited evidence which suggests how long the benefits (e.g. housing situation, health benefits or reduced service use) are expected to last for once the support is removed from those in the intervention arm. Given the uncertainties around the long-term outcomes of those in the trial, this economic evaluation will assess the value for money over the six months between baseline data collection and six-month follow up data collection. However, we note that this is likely to be an underestimate of the potential benefits of the intervention.

We anticipate that the costs of the outreach services with a health specialism programme may exceed the benefits over this short time horizon (a description of costs and benefits is below). Hence, we expect to carry out a breakeven analysis to produce an estimate of how many years service users in the intervention arm would need to remain housed for, until the benefits justified the costs. This will entail applying discount rates and taking account of inflation to determine the breakeven rate.

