#### 12.2.5. Benefits

We anticipate that the **benefits** of the intervention, scaled by the size and duration of the impact outcome can be grouped across the following categories: avoided costs associated with improved housing situations (primary outcome measure) and the (monetised) impact of the intervention on the health of the service users (secondary measure). We discuss these in turn.

---

 Breakeven analysis aligns with Cost Effectiveness Analysis in Green Book terms, enabling arguments to be made for the programme without the need for the stronger evidence requirements that relate to CBA, though it is more dependent on modelling assumptions which can be further tested in sensitivity analysis terms.

**Avoided costs.** It is anticipated that there would be a number of costs that would be avoided if someone was able to cease rough sleeping, over and above the counterfactual.

We do not think the short life cycle of the pilot permits distinguishing two types of direct benefits – ending rough sleeping and therefore going into temporary accommodation (TA); but then over time moving from TA to settled accommodation. However, for this trial we do note that moving into TA itself increases TA usage and costs and these would need to be factored into the CBA.

We also understand the lack of consensus around critical values for avoided costs more generally and note that narrowing this divergence is a priority outcome anticipated from the Test & Learn exercise as a whole – we thus expect to use the more consensual and agreed measures where it is appropriate to do so.

Pleace and Culhane (2016) undertook research to understand the use of public services by those that are homeless. Pleace and Culhane (2016) utilised qualitative interviews with 86 people experiencing homelessness for at least 90 days from across England to understand their levels of service use, which informed an estimation of associated costs. The authors then sought to understand the potential cost saving associated with moving someone from homeless to homed. This is a challenging exercise for two main reasons: firstly, there is no clear counterfactual, i.e. what the service use would be for the same person were they not homeless; and secondly, service use may partly be determined by previous experiences during homelessness. The estimated cost saving from Pleace and Culhane (2016) of going from homeless to homed is presented in the table below (Table 14).

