**Table 17: VfM Indicators and Methods**

Indicator	Data Collection Method	Analytical Method
Reduction in people who are rough sleeping – either through avoided rough sleeping or transitioning from rough sleeping to housed	Included in routine data collection. Housing outcomes drawn from the CHI adapted version of the Residential Time-Line Follow-Back (RTLFB) inventory (see Outcome Measures - Section 7).	Using regression analysis to compare intervention and control groups.
Health status	EQ5d-5L included in routine data collection (see Outcome Measures – Section 7).	Using regression analysis to compare intervention and control groups.
Interactions with health services	Questions adapted from MHCLG rough sleeping Questionnaire and included in routine data collection.	Using regression analysis to compare intervention and control groups.

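### The breakeven threshold is worded on how long intervention-arm users stay housed, not on the between-arm difference, so it can understate the payback time

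*Protocol*

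**What the plan says.** Protocol section 12.2.3 limits the value-for-money assessment to the six months between baseline and final follow-up. It then says: "We anticipate that the costs of the outreach services with a health specialism programme may exceed the benefits over this short time horizon". For that reason it expects a breakeven analysis, described as an estimate of "how many years service users in the intervention arm would need to remain housed for, until the benefits justified the costs", with discounting and inflation applied. It gives no formula and no rule for a zero or negative effect.

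Footnote 3, attached to that sentence and printed under 12.2.5, describes the breakeven route as "enabling arguments to be made for the programme without the need for the stronger evidence requirements that relate to CBA". It adds that the result leans more on modelling assumptions, which sensitivity analysis can test.

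The rest of the economic section is incremental. Section 12.2.2 says: "In the context of this trial, we consider the control arm to provide the counterfactual", and of what exceeds that counterfactual: "It is these additional benefits which represent economic and societal gains and are what we seek to understand the monetary value of". Section 12.2.5 has benefits "scaled by the size and duration of the impact outcome" and defines avoided costs as "costs that would be avoided if someone was able to cease rough sleeping, over and above the counterfactual". Table 17 obtains the housing indicator by "Using regression analysis to compare intervention and control groups". After Table 16 the protocol calls the six-month cost-benefit analysis primary and treats breakeven as something done if required.

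**The concern.** The breakeven sentence and the definitions around it describe different quantities. The sentence asks how long people in one arm stay housed. Under the protocol's counterfactual, programme costs are recovered only while more people are housed in the intervention arm than in the control arm.

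This matters in two ways. First, an analyst who follows the sentence literally credits every housed intervention user, including those who would have been housed anyway. Second, even if the size of the benefit is taken from the between-arm difference, the duration is still tied to the intervention arm. If control users are housed later, the gap closes while intervention users remain housed. The stated condition is then met but the costs are not recovered. Both faults shorten the payback time.

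Footnote 3 adds to the problem. It presents breakeven as needing less evidence than the cost-benefit analysis, although both rest on the same estimated effect on housing.

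**Working it through.** The protocol states no breakeven figure, so there is none to reproduce. What follows illustrates the size of the difference.

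**Inputs from the protocol**
- Discount rate r = 3.5% (12.2.8).
- Annual savings per person (Table 14): £398, £632, £1,294, £3,008, £14,173 and £1,412, which sum to £20,917. Without the hostel and night-shelter row (£14,173) the sum is £6,744.
- 320 users per arm, 40 per cluster, ICC 0.10 (Table 10). Design effect = 1 + 39 × 0.10 = 4.9.

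**Assumed inputs, not in the protocol**
- Cost C per eligible user: £2,500 (range £1,000 to £5,000).
- Proportions housed: 30% v 20%, and 20% v 20% for no effect.
- The 20% optimism-bias adjustment is not applied, and one discount rate is used throughout.

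**Formula.** Let S be the annual saving per housed person and q the proportion credited. Breakeven time T solves C = q × S × (1 − 1.035^−T) / ln(1.035), with ln(1.035) = 0.0344. So T = −ln(1 − x) / 0.0344, where x = 0.0344 × C / (q × S). If x is 1 or more, there is no finite T.

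**C = £2,500, S = £6,744**

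| Case | Credited proportion q | x | T (years) |
|---|---|---|---|
| 30% v 20%, all housed intervention users | 0.30 | 0.0425 | 1.26 |
| 30% v 20%, between-arm difference | 0.10 | 0.1275 | 3.97 |
| 20% v 20%, all housed intervention users | 0.20 | 0.0638 | 1.92 |
| 20% v 20%, between-arm difference | 0 | – | none |

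The two readings differ about threefold (3.97 / 1.26 = 3.1). Across costs of £1,000 to £5,000 and savings of £6,744 to £20,917, the 30% v 20% case gives 0.16 to 2.58 years when all are credited and 0.48 to 8.56 years on the difference. With 20% v 20%, crediting all gives 0.24 to 3.97 years, and the difference gives no finite value at any cost or saving.

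**Control users housed later.** Suppose the 10-point gap lasts only 3 years because control users catch up. The discounted benefit is 0.10 × £6,744 × (1 − 1.035^−3) / 0.0344 = £674.40 × 2.850 = £1,922, short of £2,500. Intervention users could remain housed for 3.97 years and costs would still not be recovered.

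**Precision.** For 30% v 20%, the standard error of the difference is √(4.9 × (0.30 × 0.70 + 0.20 × 0.80) / 320) = 0.0753. The normal-approximation 95% interval is 0.10 ± 1.96 × 0.0753 = −0.048 to 0.248. At 0.248, x = 0.0515 and T = 1.54 years. The breakeven interval therefore runs from 1.54 years to no finite value, around a point estimate of 3.97.

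**How often a finite value appears under no effect, on the between-arm reading.** Discounting sets a minimum difference of 0.0344 × C / S. This is 0.0016 at £1,000 and £20,917, and 0.0255 at £5,000 and £6,744. With an assumed 25% housed in both arms, the standard error is √(4.9 × 2 × 0.25 × 0.75 / 320) = 0.0758. The chance that the estimate exceeds the minimum is then P(Z > 0.022) = 49% down to P(Z > 0.336) = 37%.

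**The case against.** The strongest reply is that the word benefits is already defined. Sections 12.2.2 and 12.2.5 and Table 17 make it incremental to the control arm, so a zero effect gives zero benefit and no breakeven. This largely stands. A reader might infer that the plan returns a finite payback whatever the effect, or that its value-for-money conclusion does not depend on whether the intervention worked. The documents do not support either inference, because both need the reading that credits all housed users, which the surrounding definitions largely exclude. Nor is breakeven set to become the headline: the six-month analysis is primary, and a null pilot would show costs without offsetting benefits there.

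A reader might also infer that half of null pilots would give a finite payback. Discounting makes that too high: 37% to 49% under the inputs above.

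It can also be said that section 12.2.6 provides for low, central and high inputs and for confidence intervals where appropriate, that section 10.3 promises 95% intervals, that footnote 3 carries its own caveat, and that the detail may sit in an analysis plan not seen here. These points reduce the concern. They do not change the quantity that 12.2.3 names, and nothing in 12.2.6 ties an interval to it.

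Finally, breakeven is a threshold and not a forecast that housing will persist. That is correct. But a threshold is useful only if meeting it recovers the costs, and years housed in one arm does not ensure that.

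**Conclusion.** The point holds as a conflict between the wording of 12.2.3 and the counterfactual set in 12.2.2 and 12.2.5. It is worth correcting because the choice of quantity changes the answer: about threefold (1.26 v 3.97 years) under the assumed £2,500 cost, £6,744 saving and 30% v 20% housed. The ratio follows mainly from the assumed proportions (0.30 / 0.10 = 3 before discounting), so it would be larger for a smaller effect and smaller for a larger one. The direction does not depend on these inputs: whenever some control users are housed, crediting all intervention users shortens the payback. At the planned sample size, a single number of years without limits would also hide that the interval can extend to no payback at all.

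**What to change.** In 12.2.3, define breakeven as the number of years for which the adjusted between-arm difference in the proportion not homeless would have to persist for discounted additional benefits to equal costs. Take that difference, on the absolute scale, from the section 10.4 analysis. Report the result with limits from the 95% confidence interval of the difference. State that the result is no finite breakeven when the estimate is zero, negative or too small to recover costs after discounting, and use the same statement as the limit when the interval includes such values.

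Reword footnote 3 so that it does not suggest breakeven needs weaker evidence of effect than the cost-benefit analysis. A scenario in which the difference shrinks after six months as control users are housed would be useful but is optional.

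The cost is a few sentences of protocol text and a few lines in the economic model, with no new data. The drawback is that the reported figure will be less favourable and often unbounded.
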